6.4.6.1.1. Sensitivity Analysis for Primary Efficacy Endpoints

In order to support the robustness of the conclusions drawn from the co-primary efficacy analyses, we will perform the following sensitivity analyses for the co-primary efficacy endpoints.

Percentage change in LDL-C from baseline to Day 510

• A control-based pattern-mixture model (PMM), using the same imputed datasets and MMRM model that was used for the second co-primary efficacy endpoint primary analysis will be used to compare treatments at Day 510. Multiple imputations will be

used to account for uncertainty in the imputation process and results from the imputed datasets will be combined using Rubin's method. (Refer to Appendix 3 for details)

- A mixed model for repeated measurements (MMRM) analysis without multiple imputation, that assumes missing data are missing at random (MAR), will be performed. The model will include fixed effects for treatment, visit, baseline value, and the interaction between treatment and visit. The Restricted Maximum Likelihood (REML) estimation approach will be used with the covariance structure set as "Unstructured". A linear contrast at Day 510 will be used to compare treatment groups. This will be the same model that is used as a sensitivity analysis for the second co-primary endpoint.
- The impact of country and current use of statins or other lipid-modifying therapies will be assessed by including country (possibly pooled into a region), the treatment-by-country interaction, and current use of statins or other lipid-modifying therapies (yes or no) as fixed effects into the primary efficacy analysis ANCOVA (using multiple imputation washout model data).
- An ANCOVA model without multiple imputation will be performed using the mITT population. The model will include the fixed effect of treatment group and baseline LDL-C as a covariate.
- A tipping point analysis will be performed to search for the tipping point that reverses the study conclusion. In the tipping point analysis, we will independently vary the deltas in the treatment groups (inclisiran group progressively worse while the placebo group is not impacted and inclisiran group progressively worse while the placebo group progressively improves) until the hypothesis test on the co-primary efficacy endpoint becomes statistically insignificant.

Time adjusted percentage change in LDL-C from baseline after Day 90 and up to Day 540.

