- Observed value of efficacy measurement at Day 90 (continuous)
- Observed value of efficacy measurement at Day 150 (continuous)
- Observed value of efficacy measurement at Day 270 (continuous)
- Observed value of efficacy measurement at Day 330 (continuous)
- Observed value of efficacy measurement at Day 450 (continuous)

- Observed value of efficacy measurement at Day 510 (continuous)
- Observed value of efficacy measurement at Day 540 (continuous)
- Current use of statins or other lipid-modifying therapies (categorical)
- 1. Intermittent missing data in the placebo treatment group will be imputed using MCMC methods, assuming MAR. SAS PROC MI will be utilized for this step using the MCMC impute=monotone option. A total of 100 datasets will be created. These datasets will be utilized in Step #2.
- 2. The remaining missing values in the placebo group with a monotone missing data pattern will be imputed in this step. Missing data will be imputed assuming data are MAR. Only subjects in the placebo group will be utilized in this step. SAS PROC MI will be used to impute missing values utilizing the monotone reg option. This will be performed for the 100 datasets. After this step, the 100 datasets will be fully imputed for the placebo treatment group. These datasets will be utilized in Step #3.
- 3. Subjects in the inclisiran group who received all 4 doses of study medication, have the Day 510 value missing, and have evaluable data at Day 540 will be included in this step. Missing values at Day 510 will be imputed assuming data are MAR. Only subjects in the inclisiran group will be included in this step. Observed Baseline and Day 510 data will be utilized to impute missing Day 510 data utilizing SAS PROC MI. This will be performed 100 times to create 100 datasets that are fully imputed at Day 510.
- 4. The remaining missing values at Day 510 in the inclisiran group will be imputed in this step. Note that the subjects with imputed inclisiran Day 510 data from Step #3 will not be utilized in this step. Control-based PMM imputation will be performed. With this imputation model, the missing efficacy measurements in the inclisiran group will not be constructed from the observed data in the inclisiran group but rather from the observed and imputed data in the placebo group at Day 510. Baseline data will also be utilized in the imputation. The MNAR statement in SAS PROC MI will be used to impute missing values. This will be performed for the 100 datasets.

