APPENDIX 3. CONTROL-BASED PATTERN MIXTURE MODEL

A control-based Pattern-Mixture Model (PMM) will be used to explore the possibility of data missing not at random (MNAR) for subjects who discontinued the study. For subjects who discontinued the study without any further follow-up data, their missing values after study discontinuation will be imputed under the assumption that their outcome would be the similar to those in the placebo group with similar background characteristics. For subjects who did not discontinue the study, their intermittent missing values will be imputed based on the MAR assumption. Multiple imputation will be used to account for uncertainty in the imputation process and results from the imputed datasets will be combined using Rubin's method. Further details are provided below.

Windowing will be performed first (see Section 6.3.3) and any missing data will be imputed using the following steps.

The covariates and baseline characteristics which can be predictive of the response will be included in a multiple imputation procedure (SAS PROC MI) and will include the following:

- Baseline value of efficacy measurement (continuous)
- Observed value of efficacy measurement at Day 90 (continuous)
- Observed value of efficacy measurement at Day 150 (continuous)
- Observed value of efficacy measurement at Day 270 (continuous)
- Observed value of efficacy measurement at Day 330 (continuous)
- Observed value of efficacy measurement at Day 450 (continuous)
- Observed value of efficacy measurement at Day 510 (continuous)
- Observed value of efficacy measurement at Day 540 (continuous)
- Current use of statins or other lipid-modifying therapies (categorical)
- 1. Intermittent missing data will be imputed using MCMC methods, assuming MAR, within each treatment group. SAS PROC MI will be utilized for this step using the MCMC impute=monotone option. A total of 100 datasets will be created. These datasets will be utilized in Step #2.

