2.4. Statin/LMT Use at Baseline

The small number of subjects who were not currently using statins or other lipid-modifying therapies (LMT) at baseline caused convergence issues with the imputation models. As such, the statin/LMT use at baseline effect was removed from the multiple imputation washout model and Control Based - Pattern Mixture Model imputation steps. Note that the statin/LMT use at baseline effects were already removed from the analysis models.

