2.5. Appendix 2: Multiple Imputation Washout Model

Minor changes were made to the description of the multiple imputation washout model to aid in the understanding of the method. The changes did not alter the way the method was implemented. The final wording is provided below.

A multiple imputation washout model will be utilized for the primary efficacy analysis of the percentage change in LDL-C from baseline to Day 510 endpoint. The washout model can be thought of as a modified control-based Pattern-Mixture Model (PMM) that will be used to explore the possibility of data missing not at random (MNAR) for subjects who discontinued the study early. For subjects who discontinued the study early, their missing values will be imputed under the assumption that their outcome would be similar to those in the placebo group with similar background characteristics. For subjects in the inclisiran group only missing Day 510 values will be imputed. For subjects in the placebo group their missing values over all visits after early termination will be imputed based on the missing at random (MAR) assumption. Multiple imputation will be used to account for uncertainty in the imputation process and results from the imputed datasets will be combined using Rubin's method. Further details are provided below.

Windowing will be performed first (see Section 6.3.3) and any missing data will be imputed using the following steps.

For the placebo group the following variables will be included in a multiple imputation procedure (SAS PROC MI), this assumes missing data are MAR:

- Baseline value of efficacy measurement (continuous)
- Observed value of efficacy measurement at Day 90 (continuous)
- Observed value of efficacy measurement at Day 150 (continuous)
- Observed value of efficacy measurement at Day 270 (continuous)
- Observed value of efficacy measurement at Day 330 (continuous)
- Observed value of efficacy measurement at Day 450 (continuous)
- Observed value of efficacy measurement at Day 510 (continuous)
- Observed value of efficacy measurement at Day 540 (continuous)

For the subjects in the inclisiran group who completed all 4 doses and have data present at Day 540 (considered to have completed the study) the following variables will be included in a multiple imputation procedure (SAS PROC MI), this assumes missing data are MAR:

- Baseline value of efficacy measurement (continuous)

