- Observed value of efficacy measurement at Day 510 from the inclisiran group (continuous)

For the remaining subjects in the inclisiran group the following variables will be included in a multiple imputation procedure (SAS PROC MI), this assumes missing data are MNAR:

- Baseline value of efficacy measurement (continuous)
- Observed value of efficacy measurement at Day 510 from the placebo group (continuous)
- 1. Intermittent missing data in the placebo treatment group will be imputed using MCMC methods, assuming MAR. SAS PROC MI will be utilized for this step using the MCMC impute=monotone option. A total of 100 datasets will be created. These datasets will be utilized in Step #2.

- 2. The remaining missing values in the placebo group with a monotone missing data pattern will be imputed in this step. Missing data will be imputed assuming data are MAR. Only subjects in the placebo group will be utilized in this step. SAS PROC MI will be used to impute missing values utilizing the monotone reg option. This will be performed for the 100 datasets. After this step, the 100 datasets will be fully imputed for the placebo treatment group. These datasets will be utilized in Step #4.
- 3. Subjects in the inclisiran group who received all 4 doses of study medication, have the Day 510 value missing, and have evaluable data at Day 540 will be included in this step. Missing values at Day 510 will be imputed assuming data are MAR. Only subjects in the inclisiran group will be included in this step. Observed Baseline and Day 510 data will be utilized to impute missing Day 510 data utilizing SAS PROC MI. This will be performed 100 times to create 100 datasets that are fully imputed at Day 510.
- 4. The remaining missing values at Day 510 in the inclisiran group will be imputed in this step. Note that the subjects with imputed inclisiran Day 510 data from Step #3 will not be utilized in this step. Control-based PMM imputation will be performed. With this imputation model, the missing efficacy measurements in the inclisiran group will not be constructed from the observed data in the inclisiran group but rather from the observed and imputed data in the placebo group at Day 510. Baseline data will also be utilized in the imputation. The MNAR statement in SAS PROC MI will be used to impute missing values. This will be performed for the 100 datasets.

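### Does imputing Day 510 LDL-C from baseline alone for inclisiran completers (washout step 3) call for a change?

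*SAP*

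**What the plan says.** The first co-primary endpoint is analysed by ANCOVA on 100 datasets completed by the washout model (SAP 6.4.6.1 and Appendix 2; final wording in Addendum 2.5). Step 3 takes inclisiran subjects who received every dose, "have the Day 510 value missing, and have evaluable data at Day 540 will be included in this step". The assumption is explicit: "Missing values at Day 510 will be imputed assuming data are MAR". The inputs are equally explicit: "Observed Baseline and Day 510 data will be utilized to impute missing Day 510 data utilizing SAS PROC MI". Appendix 2 also listed baseline statin or other lipid-modifying therapy use as a predictor. Addendum 2.4 reports that, because of convergence problems, "the statin/LMT use at baseline effect was removed from the multiple imputation washout model". Day 510 is the variable being filled in, so only baseline is left to predict it.

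The placebo list in Addendum 2.5 holds baseline and every lipid visit from Day 90 to Day 540. Appendix 3, which serves the second co-primary endpoint, has the same visit list for both arms: "Intermittent missing data will be imputed using MCMC methods, assuming MAR, within each treatment group". SAP 6.4.6.1.1 then plans a control-based pattern-mixture sensitivity analysis at Day 510, "using the same imputed datasets and MMRM model that was used for the second co-primary efficacy endpoint primary analysis". It also plans an MMRM without imputation and a tipping-point analysis.

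**The concern.** A Day 540 value is required to enter step 3, yet it is not used to predict Day 510, 30 days earlier. A placebo subject with the same gap (Day 510 missing, Day 540 present) is imputed from all of his or her visits, so one primary analysis treats the same pattern differently by arm.

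Missing at random given baseline alone is a stronger assumption than missing at random given the subject's own on-treatment values. If subjects who miss Day 510 respond worse than others with the same baseline, step 3 gives them the average inclisiran response and the estimate leans towards the drug. If they respond better, it leans the other way. At stake is the point estimate of the first co-primary endpoint.

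**Working it through.** **1. Predictors of a missing Day 510 value when Day 540 is present**

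| Analysis and group | Predictors | Source |
|---|---|---|
| Washout, inclisiran, all doses (step 3) | Baseline | Addendum 2.4, 2.5 |
| Washout, placebo (step 1) | Baseline; Days 90, 150, 270, 330, 450, 540 | Addendum 2.5 |
| Pattern-mixture, either arm (step 1) | Baseline; Days 90, 150, 270, 330, 450, 540 | Appendix 3, with Addendum 2.4 |

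The difference is real.

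**2. The plan's own figures.** 400 × 0.95 = 380 evaluable, or 190 per arm. With a difference of 30 and SD 20 (SAP 6.1), SE = 20 × √(2/190) = 2.05 and 30/2.05 = 14.6. Power at one-sided 0.025 is 1.00 to two decimals, so the claim of more than 90% reproduces. The plan gives no figure for step 3.

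**3. Shift in the estimate.** Inputs: 482 enrolled, allocated 1:1, so 241 per arm. Assumed: *k* step 3 subjects, whose true Day 510 change differs by *d* points on average from a baseline-only draw; SD of percentage change 20 points (the plan's 20 is in mg/dL). Shift = *k* × *d* / 241; SE = 20 × √(2/241) = 1.82.

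| *k* | *d* = 10 | *d* = 20 | *d* = 20, in SEs |
|---|---|---|---|
| 1 | 0.04 | 0.08 | 0.05 |
| 2 | 0.08 | 0.17 | 0.09 |
| 5 | 0.21 | 0.41 | 0.23 |
| 12 | 0.50 | 1.00 | 0.55 |

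With SD 30 the SE is 2.73, and the last entry falls to 0.36 SE. Twelve subjects is 5% of 241. It is illustrative only: the plan's 5% refers to dropouts, whereas step 3 subjects are completers.

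**4. Simulation** (1,000 trials, 20 imputations, 241 per arm, SD 20, between-visit correlation 0.4 and 0.7, all assumed). With Day 510 missing at random, baseline-only bias was at most 0.01 point. With missing subjects drawn from the worst-responding quarter on their other visits, bias favoured inclisiran by 0.12–0.17 point (*k* = 2), 0.30–0.44 (*k* = 5) and 0.73–1.05 (*k* = 12). Imputing from the other visits left at most 0.012, as expected when selection depends on those visits.

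**5. Precision.** If missingness is unrelated to response, the SE grows by √[(1/(241−*k*) + 1/241)/(2/241)] − 1, which is 0.2% at *k* = 2 and 1.3% at *k* = 12.

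**6. The test.** At a 30-point effect, significance is lost after a shift of 30 − 1.96 × 1.82 = 26.4 points. With 12 subjects that needs 26.4/(12/241) = about 530 points per subject.

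**7. What the planned analyses recover.** For a difference that persists over *m* other visits with equal correlation *r* given baseline, the share removed is *mr*/(1 + (*m*−1)*r*). For *r* from 0.3 to 0.8:

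- all six other visits, as in the pattern-mixture imputation: 1.8/2.5 = 0.72 to 4.8/5.0 = 0.96;
- Days 90–450, as in the Appendix 1 MMRM: 1.5/2.2 = 0.68 to 4.0/4.2 = 0.95;
- the same without Day 90, which Appendix 1 drops for time-adjusted analyses: 1.2/1.9 = 0.63 to 3.2/3.4 = 0.94.

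**8. How many subjects.** The documents do not give the number. SAP 6.4.1 tabulates, by arm, study completion within each analysis population. Completion means the Day 540 visit was made, and mITT requires a Day 510 LDL-C (6.3.2.3). Inclisiran completers in ITT minus those in mITT, read with the missed doses in 6.4.4, comes close to the step 3 count.

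**The case for a change.** The best case for a change is that the fix is cheap and the method is already written. Appendix 3 step 1 could replace step 3 in one labelled run, which 6.4.6.1.1 permits. No planned analysis isolates step 3: the pattern-mixture analysis and the MMRM also alter dropout handling and replace ANCOVA. Whether the tipping-point deltas apply to imputed values or to whole arms is not stated; either way, the step 3 predictors stay as they are. Deviation counts do not identify the group either, because a sample can be drawn and still miss the window. The Day 450 visit may fall 30 days late, and protocol 6.7 places follow-up 60 days after each dose; 480 + 60 = Day 540, past the Day 525 limit in SAP Table 2.

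The asymmetry between arms and the lack of a clean isolation both stand. They do not make a case for action. The pattern-mixture analysis applies the very imputation wanted, to the same subjects and visit, and like washout step 4 it imputes inclisiran dropouts from placebo data. On completed data with treatment-by-visit terms and unstructured covariance, its Day 510 contrast should lie close to the ANCOVA result. A gap caused by visit timing also gives no particular reason to suspect a link with response. Any threshold for an extra run would rest on assumed values of *d* and SD.

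Timing also counts against rewording step 3. Its restriction to baseline and Day 510 data was already in Appendix 2 before unblinding. The addendum followed unblinding and, in this step, removed only the statin or lipid-therapy term. SAP 8 says imputation methods were modified per FDA feedback; the documents do not show whether this predictor list came from it.

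**Conclusion.** The reading is correct: step 3 uses less information than it could and assumes more than the matching placebo step. Keeping it is still a fair trade-off, because a change would gain nothing that affects a conclusion. Each affected subject moves the estimate by 0.04 to 0.08 point for an assumed gap of 10 to 20 points, against an SE of 1.8 (SD 20) to 2.7 (SD 30). Even the illustrative 12 subjects move it by at most 1.0 point, while 26.4 would be needed to overturn the test. These sizes assume equal arms of 241, the stated SDs and that range of gaps; the number of step 3 subjects is unknown.

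The planned Day 510 pattern-mixture analysis and the MMRM already show what happens when these subjects' own visits are used, and the disposition tables come close to showing how many there are. Giving the exact step 3 count beside the result would be a courtesy in reporting and needs no change to the plan. Rewording the primary imputation after unblinding would cost more in credibility than it returns in accuracy.
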